5.9 Subject Replacement Strategy

A subject who discontinues from the trial will not be replaced.

5.10 Beginning and End of the Trial

The overall trial begins when the first subject signs the informed consent form. The overall trial ends when the last subject completes the last study-related phone-call or visit, discontinues from the trial or is lost to follow-up (i.e. the subject is unable to be contacted by the investigator).

5.11 Clinical Criteria for Early Trial Termination

The clinical trial may be terminated early if the extent (incidence and/or severity) of emerging effects/clinical endpoints is such that the risk/benefit ratio to the trial population as a whole is unacceptable. In addition, further recruitment in the trial or at (a) particular trial site(s) may be stopped due to insufficient compliance with the protocol, GCP and/or other applicable regulatory requirements, procedure-related problems or the number of discontinuations for administrative reasons is too high.

At 75% of the CV death events, a futility interim analysis is planned and the DSMB may recommend early termination of the trial due to the lack of efficacy of vericiguat. Also at 75% of the CV death events, an efficacy interim analysis is planned and the DSMB may recommend early termination of the trial if clear and consistent efficacy is observed for vericiguat.

6.0 TRIAL FLOW CHART

Trial Period	Screening		Treatment								Premature Treatment Discontinuation ^l		
	1 Screen ^a	2 Rand ^b	3	4	5	6	7	Visit _n ^c	Final Visit ^d	Final Phone Contact ^e	Discon Visit ^g	Safety Follow-up Visit ^h	Cont. through end of trial ^l
Visit Number/Title:	Day -30 to -1	Day 1	Day 14	Day 28	Week 16 (Month 4)	Week 32 (Month 8)	Week 48 (Month 12) and Yearly ^j	Every 16 weeks	At time of Efficacy Cut-off	14 days after Final Visit	At time of permanent treatment discon	14 days from last dose	Every 16 weeks
Scheduled Days/Week/Month:													
Scheduling Window Days/Weeks/Months:			±4 days	±4 days	±2 weeks	±2 weeks	±2 weeks	±2 weeks		+1 week		+1 week	±2 weeks
Administrative Procedures													
Informed Consent	X												
Informed Consent for Future Biomedical Research	X												
Informed Consent for Imaging Substudies ^{v,w}	X												
Demographics & Medical History	X												
Inclusion/Exclusion Criteria	X	X											
Subject Identification Card	X	X											
Prior and Concomitant Medication Review	X	X	X	X	X	X	X	X	X		X	X	X
Treatment Randomization		X											
MK-1242 or Placebo Administration/Dispensing ^k		X	X	X	X	X	X	X					
Clinical Procedures/Assessments													
Height		X											
Weight		X	X	X	X	X	X	X	X		X	X	X
Physical Exam ^l		X						X	X		X		
Electrocardiogram (12 Lead) ^s		X			X				X		X		
Vital Signs (Pulse, BP) ^m	X	X	X	X	X	X	X	X	X		X	X	X
Dose Assessment ^y			X	X	X	X	X	X					
NYHA Classification	X	X	X	X	X	X	X	X	X		X	X	X
CCSA ^z	X												
QOL Questionnaires (KCCQ & EQ-5D)		X		X	X	X	X		X		X	X	
Trial Medication Compliance			X	X	X	X	X	X	X		X		
Clinical Events Assessment ^{aa}			X	X	X	X	X	X	X	X	X	X	X
Adverse Events Monitoring	X	X	X	X	X	X	X	X	X	X	X	X	
Vital Status ⁿ										X ⁿ			
Echocardiogram ^y		X				X							
Cardiac Magnetic Resonance Imaging ^w		X				X							
Submission of Hospitalization Details (US subjects only) ^{bb}		X	X	X	X	X	X	X	X	X	X	X	X

Trial Period	Screening		Treatment								Premature Treatment Discontinuation ^l		
	1 Screen ^a	2 Rand ^b	3	4	5	6	7	Visit _n ^c	Final Visit ^d	Final Phone Contact ^e	Discon Visit ^g	Safety Follow-up Visit ^h	Cont. through end of trial ^l
Visit Number/Title:	Day -30 to -1	Day 1	Day 14	Day 28	Week 16 (Month 4)	Week 32 (Month 8)	Week 48 (Month 12) and Yearly ^j	Every 16 weeks	At time of Efficacy Cut-off	14 days after Final Visit	At time of permanent treatment discon	14 days from last dose	Every 16 weeks
Scheduling Window Days/Weeks/Months:			±4 days	±4 days	±2 weeks	±2 weeks	±2 weeks	±2 weeks		+1 week		+1 week	±2 weeks
Local Laboratory Assessments													
Creatinine (calculation of eGFR ^o)	X												
BNP/NT-proBNP ^o	X												
Central Laboratory Assessments													
NT-proBNP ^p		X			X	X	X		X ^u		X		
Hematology		X			X	X	X		X ^u		X	X	
Chemistry		X			X	X	X		X ^u		X	X	
Liver Function Tests		X			X	X	X		X ^u		X	X	
Hemoglobin A1c ^q		X			X	X	X		X ^u		X		
Urine Pregnancy Test ^r		X			X	X	X	X	X ^u		X		
Blood for Genetic Analysis ^s		X											
Blood for PK evaluation ^t		X			X		X		X ^u		X		
Blood for Biomarkers		X			X	X			X ^u		X		

- a. Screening can start as early as at time of hospitalization or upon intravenous diuretic treatment for heart failure.
- b. Screening visit and Randomization (Visit 2) can occur on the same day if the subject is clinically stable as defined as having not received IV treatment for > 24 hours and having SBP ≥ 100 mmHg. In this case, all procedures specified for Visit 2 must be done after informed consent is given and will replace screening visit procedures.
- c. V_n: Starting from Visit 7 (Week 48) all subsequent visits will be scheduled at 16 ±2 week intervals until study completion is reached.
- d. The Final visit will be conducted for all subjects (including those who prematurely discontinued study treatment) when the planned number of CV death events is reached and the efficacy cut-off is announced by the Sponsor.
- e. All subjects will be contacted by phone within 14 days (+ 1 week) of the Final visit to assess for clinical events, adverse events, and vital status (if applicable).
- f. Premature treatment discontinuation visits are relevant to subjects who **permanently** discontinue study treatment. These visits do not apply to subjects who temporarily interrupt study treatment.
- g. Discontinuation visits will be conducted at the time of permanent treatment discontinuation for the collection of clinical events, adverse events, and other procedures listed.
- h. In-clinic safety follow-up visit required for all subjects who permanently discontinue study treatment prematurely. Visit to be conducted within 14 days (+ 1 week) after last dose study treatment.
- i. Subjects who permanently discontinue treatment prematurely will continue in-clinic visits every 16 weeks, including the Final Visit and Final Phone Contact.
- j. Procedures completed at Week 48 and at each yearly visit until study completion.
- k. Dose assessment based on criteria described in Section 5.2.1.2.
- l. Complete physical exam completed at Visit 2. Directed physical exams to be completed at Week 48 (Visit 7), subsequent Yearly visits, and the Premature Discontinuation Visit and/or Final Visit.
- m. Three measurements, each approximately 2 min apart. Visit 2: Prior to and at 2 ±0.5h post study-drug dosing; Visit_n until Final visit: vital sign measurement is only needed prior to study drug dosing. Blood Pressure and pulse rate measurements should be performed as described in Appendix 12.5
- n. This assessment can be performed at any point in the trial when vital status is in question.
- o. Local laboratory creatinine and NT-proBNP or BNP within 30 days before randomization will be entered in eCRF to confirm eligibility. The creatinine assessed at this time will be used to calculate eGFR by MDRD equation. Recent historical local laboratory assessments may be used provided these assessments were obtained within 30 days before randomization.
- p. NT-proBNP measurements assessed by the central lab will be blinded after Visit 2.
- q. Hemoglobin A1c to be evaluated in diabetic subjects only.
- r. In case of positive urine pregnancy test, a confirmatory serum test will be done. A negative result is required for randomization.
- s. Refer to section 7.1.3.4 for sample collection information.
- t. In case the PK sample at the specified visits cannot be obtained at a specified time point, the sample can be taken at the subsequent visits within the year of treatment. Exact collection date/time of the

Trial Period	Screening		Treatment								Premature Treatment Discontinuation ^f		
	1 Screen ^a	2 Rand ^b	3	4	5	6	7	Visit ⁿ ^c	Final Visit ^d	Final Phone Contact ^e	Discon Visit ^g	Safety Follow-up Visit ^h	Cont. through end of trial ⁱ
Visit Number/Title:	Day -30 to -1	Day 1	Day 14	Day 28	Week 16 (Month 4)	Week 32 (Month 8)	Week 48 (Month 12) and Yearly ^j	Every 16 weeks	At time of Efficacy Cut-off	14 days after Final Visit	At time of permanent treatment discon	14 days from last dose	Every 16 weeks
Scheduled Days/Week/Month:													
Scheduling Window Days/Weeks/Months:			±4 days	±4 days	±2 weeks	±2 weeks	±2 weeks	±2 weeks		+1 week		+1 week	±2 weeks

PK samples and date/time of last study drug intake (either at home on the day before the sample or at site) must be documented.

- u. Not applicable for subjects who prematurely discontinue from study treatment.
- v. At sites participating in the imaging substudies, subjects may elect to participate in an echocardiography substudy as described in Section 7.1.6.1. The baseline echocardiogram should be performed prior to study drug administration and may be performed over the course of the screening period.
- w. At sites participating in the imaging substudies, subjects may elect to participate in a cardiac magnetic resonance imaging substudy as described in Section 7.1.6.1. The baseline cardiac magnetic resonance imaging should be performed prior to study drug administration and may be performed over the course of the screening period.
- x. At each scheduled ECG assessment, sites should print 2 original paper tracings. One original paper tracing should be maintained in subject files and second original paper tracing should be mailed to the core ECG vendor (batched once monthly).
- y. Dose assessment to be performed at all scheduled and unscheduled visits when BP is assessed.
- z. Performed only in subjects with a medical history of active stable angina.
- aa. Clinical Events Assessment includes an assessment for the occurrence of study endpoint events as described in Sec. 7.3.4.
- bb. At US sites participating in the Health Economics Outcomes Research analysis, hospital billing information will be obtained to inform a cost-effectiveness analysis.

Abbreviations: CCSA = Canadian Cardiovascular Society Functional Classification of Angina EQ-5D = EuroQol Group 5-dimension, 5-level questionnaire; KCCQ= Kansas City Cardiomyopathy Questionnaire; NYHA = New York Heart Association; ECG = electrocardiogram; BP = blood pressure; NT-proBNP = N-terminal brain natriuretic peptide; PK=pharmacokinetics; QoL=quality of Life; eGFR=estimated Glomerular Filtration Rate; US = United States

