3.3 Other Objectives (Exploratory)

In subjects with HF_{rEF} on a background of standard of care:

- (1) **Objective:** To evaluate the efficacy of MK-1242 (vericiguat) in comparison to placebo in increasing the time to HF event, defined as composite of HF hospitalization or urgent HF visit (not meeting the criteria for a HF hospitalization).

- (2) **Objective:** To evaluate the efficacy of MK-1242 (vericiguat) in comparison to placebo in increasing the time to first CV hospitalization.

- (3) **Objective:** To evaluate the efficacy of MK-1242 (vericiguat) in comparison to placebo in reducing the total number of HF hospitalizations.

- (4) **Objective:** To evaluate the efficacy of MK-1242 (vericiguat) in comparison to placebo on the change in health-related quality of life summary measures (Kansas City Cardiomyopathy Questionnaire [KCCQ] and EuroQol Group 5-Dimensional [EQ-5D]) from baseline to each measured time point.

- (5) **Objective:** To explore the relationship between genetic variation and response to the treatment administered. Variations across the human genome may be analyzed for association with clinical data collected in this study.

- (6) **Objective:** To explore relationship between baseline blood biomarker levels and response to treatment and the effect treatment has on established and emerging blood biomarkers.

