Study drug discontinuation for any reason does not represent withdrawal from the study. Since data on clinical events and vital status are essential to the primary analysis, they must be collected until the end of the study, even if the subject discontinued study drug treatment. Therefore, all efforts will be taken to obtain data on clinical events and vital status until the end of study.

Thus, subjects who permanently discontinue study drug will still be followed for clinical events and vital status until study completion. They should attend all scheduled protocol-defined visits and study procedures as provided in the visit schedule (Section 6.0) just as those who remain on study drug. If the subject does not attend scheduled study visits, follow-up of clinical events specified as endpoints may continue by phone, unless the subject

explicitly withdraws his/her consent to any type of follow-up. In such cases, the phone contact will not be considered a protocol deviation.

At any time a subject's vital status is in question, the investigator should explore all possible options to contact the subjects per local regulations (unless the subject has explicitly withdrawn his/her consent to any type of follow-up). The site must document all attempts to try to contact the subjects in the medical records/source documents. The vital status will be collected for all randomized subjects who have not withdrawn consent, irrespective of completion of study procedures.

In all cases, the reason for temporary interruption or permanent study drug discontinuation must be recorded in the electronic case report form (eCRF) and in the subject's medical records.

Subjects may be allowed to begin treatment/vaccination again if deemed medically appropriate, unless he/she has been unblinded.

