7.1.5.3.2 Safety follow-up Visit

An in-clinic safety follow-up visit will be conducted for all subjects who discontinue study drug prematurely. This visit will be conducted within 14 days + 1 week after last dose of study treatment. Subjects who discontinue treatment prematurely will continue to attend all protocol specified visits and perform all procedures stipulated in that visit, including the Final visit, except in case the subject specifically withdrew consent for further follow-up and no additional information is permitted to be collected. If the subject does not attend the study visit, a telephone contact for collection of protocol defined endpoint events should occur. In such cases, the phone contact will not be considered a protocol deviation.

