8.4.1 Efficacy Endpoints

Primary Endpoint

The primary endpoint of the study is the time to the first occurrence of the composite endpoint of CV death or HF hospitalizations. Subjects without a HF hospitalization or CV death at the time of analysis will be censored at time of non-CV death or time of last information available during the pre-specified follow-up period for subjects still alive at time of analysis. Only clinical events confirmed by CEC will be used to define the primary endpoint.

Secondary Endpoints

The secondary study endpoints are:

- Components of the primary composite endpoint:
 - Time to CV death
 - Time to first HF hospitalization
- Time to total HF hospitalizations (first and recurrent)
- Time to first occurrence of the composite of all-cause mortality or HF hospitalization
- Time to all-cause mortality

Exploratory Endpoints

The following endpoints will be considered outside of the testing procedure and considered as exploratory endpoints:

- Time to first HF event, defined as composite of HF hospitalization or urgent HF visit (not meeting the criteria for a HF hospitalization).
- Time to first CV hospitalization
- Total number of HF hospitalizations
- Change from baseline in health-related quality of life measures (KCCQ and EQ-5D)

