8.5 Analysis Population

The primary endpoint analysis will use the Intention-to-Treat (ITT) population. The ITT population includes all randomized subjects. The subjects will be analyzed according to the planned treatment. Subjects without any post-randomization information will be censored at Day 1.

The ITT population will also be used for the secondary and exploratory efficacy endpoints analyses. The subjects will be analyzed according to the planned treatment. Subjects without any post-randomization information will be censored at Day 1 for time to event endpoints.

The All-Subjects-as-Treated (ASaT) population will be used for safety analyses. The ASaT population includes all subjects who have taken at least one dose of study drug (vericiguat or placebo). All subjects will be analyzed according to the actual treatment received. Any subjects in ASaT who received both placebo and vericiguat during the study by mistake will be analyzed according to the planned treatment.

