8.9 Determination of Sample Size

The sample size estimation is based on a 1:1 randomization and a study-wise one-sided significance level of 0.025. In accordance with the planned interim analysis, the nominal one-sided significance level will be 0.0242 at the final analysis. A conservative approach of power calculation based only on the final analysis is used.

The study will be an event-driven study. It is planned to accrue subjects during 30 months and have a follow-up of 9 months after the last subject is included in the study. This leads to total study duration of 39 months. It is assumed that setting up of all sites will take approximately 12 months, assuming a quadratic ramp-up function for subject accrual.

The primary analysis will be performed in the ITT population. Every effort will be made to follow-up subjects that prematurely stop study medication to collect at least information for the primary endpoint (i.e. information on hospitalizations and death).

It is assumed that 2% of subjects per year will prematurely stop study medication and either object to further follow-up or be lost to follow-up, despite efforts to contact them. In addition, it is assumed that approximately 10% per year of subjects will stop study treatment and can be followed up off treatment for the primary endpoint. When a subject in the placebo group stops treatment prematurely, it is assumed that the hazard for CV death and HF hospitalization does not change, as the subject is expected to continue with standard heart failure therapy. For vericiguat subjects stopping treatment prematurely, it is assumed that they switch to the hazard of the placebo group, as they henceforth will switch back to

standard heart failure therapy. These effects will dilute the observed treatment effect when the ITT analysis approach is used. The sample size calculations are adjusted for this dilution.

The sample size calculation is driven by the CV death component of the composite primary endpoint. For the CV death component, the expected event rate in the comparator group after 12 months is 11%. The relative risk reduction with vericiguat is assumed to be 20%, relating to a HR of 0.8. Using the log-rank test, a sample size of 4872 subjects and a total of 782 CEC confirmed CV deaths will be required to achieve 80% power.

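### KCCQ and EQ-5D are not scheduled at the 16-weekly visits after permanent treatment discontinuation, so quality-of-life data go missing by design according to whether a subject stopped drug

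*Combined protocol and SAP*

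**What the plan says.** The flow chart in Section 6.0 has a row "QOL Questionnaires (KCCQ & EQ-5D" and gives subjects who permanently discontinue treatment three columns of their own: a discontinuation visit, a safety follow-up visit, and continued follow-up every 16 weeks to the end of the trial. The questionnaire row is marked in the first two and blank in the third. Footnote i makes the third column real clinic attendance: "Subjects who permanently discontinue treatment prematurely will continue in-clinic visits every 16 weeks, including the Final Visit and Final Phone Contact". Concomitant medication, weight, vital signs, NYHA class and clinical events are all marked there. The Final Visit questionnaire still applies to these subjects, because the footnote exempting them (u) is attached only to central laboratory rows.

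Two text sections speak to procedures off drug. Section 5.8 says these subjects should "attend all scheduled protocol-defined visits and study procedures as provided in the visit schedule (Section 6.0) just as those who remain on study drug". Section 7.1.5.3.2 says they "will continue to attend all protocol specified visits and perform all procedures stipulated in that visit, including the Final visit".

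On the analysis side, Section 3.3 sets the quality-of-life objective as change "from baseline to each measured time point", Section 8.4.1 places it among endpoints "considered outside of the testing procedure and considered as exploratory endpoints", and Section 8.5 adds: "The ITT population will also be used for the secondary and exploratory efficacy endpoints analyses".

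**The concern.** At Weeks 16, 32, 48 and yearly, a subject on drug is due a questionnaire and a subject who has stopped is not, although both are followed in clinic. Missingness is therefore built into the schedule and tied to an event after randomization that may itself relate to health status and to treatment arm. An ITT comparison at those weeks must either leave out the subjects who stopped, and so describe mainly those still on drug, or rely on a model joining their scores around discontinuation to the Final Visit score. The KCCQ has a 2-week recall period (Section 7.1.2.6.1), so a score taken around stopping does not describe the subject's state months later.

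The wording also leaves room for sites to differ. One that reads Section 5.8 literally may give the questionnaires at Weeks 16, 32 and 48; one that follows the dedicated column will not.

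**Working it through.** The plan states no quality-of-life sample size or missing-data rate, so there is no figure to reproduce. The check reads the chart and then sizes the gap.

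**Reading the chart.** Counted across the thirteen visit columns, the questionnaire row is marked at Randomization, Day 28, Week 16, Week 32, Week 48/yearly, Final, Discontinuation and Safety Follow-up. It is blank in the on-drug column for other 16-weekly visits and in the off-drug continuation column. The difference between subjects on and off drug therefore arises at Weeks 16, 32, 48 and yearly (and at Day 28 for very early stoppers), not at every 16-weekly visit. With visits 16 weeks apart, the first yearly visit after Week 48 is taken as Week 96.

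**Inputs from Section 8.9.** "approximately 10% per year of subjects will stop study treatment and can be followed up off treatment for the primary endpoint"; a further 2% per year stop and are lost to or refuse follow-up; 4872 subjects 1:1, so 2436 per arm; placebo CV death 11% at 12 months, hazard ratio 0.8; 74% with at least 12 months and 47% with at least 18 months of follow-up; median follow-up 532 days.

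**Share affected.** Reading 10% as an annual probability that is constant over time and independent of death, the share off drug among those in follow-up at week w is 1 − 0.90^(w/52). Some of these subjects will have a discontinuation or safety questionnaire inside the ±2-week visit window. The safety visit falls 2-3 weeks after the last dose, so this credit applies to those who stopped within the previous 4-5 weeks. Replacing w by w − 5 or w − 4 gives the share with no score in the window.

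| Week | Off drug | No score in window | Lost, 1 − 0.98^(w/52) |
|---|---|---|---|
| 16 | 3.2% | 2.2-2.4% | 0.6% |
| 32 | 6.3% | 5.3-5.5% | 1.2% |
| 48 | 9.3% | 8.3-8.5% | 1.8% |
| 96 | 17.7% | 16.8-17.0% | 3.7% |

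Reading 10% as a constant rate instead gives 8.8% at Week 48. On these inputs, the schedule removes more quality-of-life data after discontinuation than loss to follow-up does. Week 96 concerns a minority, since only 47% are expected to reach even 18 months.

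**Number of subjects at Week 48, per arm.**
- Using the plan's follow-up: 0.74 × 2436 = 1803. Then 1803 × 9.27% = 167, or 1803 × 8.34% = 150 with the window credit. The 74% refers to 12 months, slightly beyond Week 48, so these are a little low.
- Ignoring staggered entry: 2436 × exp[−(CV death + loss + non-CV death) × 48/52]. Annual hazards are −ln 0.89 = 0.1165 for placebo CV death (0.0932 on vericiguat) and −ln 0.98 = 0.0202 for loss. Non-CV death is not given, so 0-4% per year is assumed (0 to 0.0408). This leaves 2068-2194 in follow-up, and × 9.27% gives 192-203.

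**Example.** Median follow-up is 532/7 = 76 weeks. A subject who stops at Week 16 has a safety questionnaire at about Week 18-19 and no other until the Final Visit at Week 76. The gap is 57-58 weeks and covers Weeks 32 and 48.

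**The case against.** The strongest reply is that Sections 5.8 and 7.1.5.3.2, read plainly, keep discontinued subjects on the same procedures as everyone else, so this is only a wording inconsistency. But Section 5.8 refers to the schedule in Section 6.0, and Section 7.1.5.3.2 to whatever each visit stipulates. The chart has a column for exactly these visits, and the questionnaires are not in it. The two sections do not restore them, though a site could read 5.8 otherwise.

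Second, the blank may be deliberate. The off-drug column resembles the routine on-drug 16-weekly visit, which also has no questionnaire, and laboratory, PK and biomarker samples are dropped off drug too. That is fair as to intent. It does not remove the effect, because subjects on drug have the Week 16, 32, 48 and yearly visits as well.

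Third, one empty cell in a chart is thin evidence: the physical-examination row puts its mark in a different column from the one its own footnote implies. Caution is reasonable, but the questionnaire row aligns with its neighbours.

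Fourth, Section 7.1.6.2 refers to a separate health-economics plan covering patient-reported outcomes, and Section 8.6.1 leaves supportive missing-data analyses to a supplemental SAP. Either may describe how gaps are handled; neither can recover questionnaires that were never given.

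Fifth, the numbers are upper figures. Some of the 10% may be followed only by phone, and subjects without a validated translation are exempt. The 57-58-week gap is an illustration: only 3.2% are expected to have stopped by Week 16. These points stand, as does the fact that no bias has been demonstrated.

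**Conclusion.** The concern holds. Followed as written, the flow chart makes quality-of-life data at Weeks 16, 32, 48 and yearly missing by design for subjects who have stopped drug, while the stated analysis is ITT change from baseline at those points. Under the plan's own stopping rate, about 8-9% of subjects in follow-up at Week 48 are affected. The size rests on a constant stopping rate that is equal in both arms and unrelated to death. The documents give no score means, standard deviations or stopping rates by arm, so neither the direction nor the size of any bias can be stated. The endpoint is exploratory, and the primary and secondary analyses do not depend on it. This is a worthwhile low-cost improvement, not a threat to the trial's conclusions.

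**What to change.** In Section 6.0, mark KCCQ and EQ-5D in the continued-follow-up column for subjects off treatment. Add a footnote limiting collection to the visits nearest Weeks 16, 32, 48 and yearly, counted from randomization; an unqualified mark would mean every 16 weeks, more often than on drug. State in the analysis section that these scores enter the ITT quality-of-life analysis with their actual dates. Align Sections 5.8 and 7.1.5.3.2 with the revised chart.

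The cost is one chart entry and a footnote, plus a KCCQ of 5-8 minutes and an EQ-5D at clinic visits already planned. There are limits. If off-treatment visits do not fall on the original calendar, the nearest one may lie up to 8 weeks from the nominal week, or 10 with the ±2-week window. Subjects followed only by phone may still be missed. The change should come while subjects are still being followed, because scores not collected cannot be obtained later.
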